#### 6.1.1 Investigational and control drugs

**Table 6-1** Investigational and control drug

Investigational/ Control Drug(Name and Strength)	Pharmaceutical Dosage Form	Route of Administration	Supply Type	Sponsor (global or local)
MIJ821 20mg Lyophilisate in vial	powder for solution for infusion	Intravenous use (after reconstitution)	Open label supply, vials (one vial per kit)	Sponsor (global)
Placebo	0.9% sodium chloride solution	Intravenous use	Open label, infusion bag	Locally by site

The investigational treatment for this study will be MIJ821. Due to the difference in preparation between MIJ821 and placebo and the requirement for the intravenous MIJ821 dose to be prepared on a mg/kg basis for intravenous infusion for the active treatment arms, an unblinded qualified site personnel, independent of the investigational staff, is required to maintain the blind. Please refer to [Section 6.4](#) for additional details.

#### 6.1.2 Additional study treatments

No other pharmacological treatment beyond investigational drug, control drug (placebo) and antidepressant pharmacological SoC are included in this study. Patients are also allowed psychotherapy.

### 6.1.3 Treatment arms/group

This study consists of seven treatment arms, participants will be randomized in a 2:1:2:2:2:2:2 ratio on Day 1 to the following treatment arms on the top of the ongoing SoC:

- Placebo, one infusion every other week on Day 1, Day 15 and Day 29 of treatment (Core Period only)
- MIJ821 fixed dose of 0.0048 mg/kg, one infusion every other week on Day 1, Day 15 and Day 29 of treatment/ relapse retreatment
- MIJ821 fixed dose of 0.016 mg/kg, one infusion every other week on Day 1, Day 15 and Day 29 of treatment/ relapse retreatment
- MIJ821 fixed dose of 0.048 mg/kg, one infusion every other week on Day 1, Day 15 and Day 29 of treatment/ relapse retreatment
- MIJ821 fixed dose of 0.16 mg/kg, one infusion every other week on Day 1, Day 15 and Day 29 of treatment/ relapse retreatment
- Single administration MIJ821 0.048 mg/kg, one infusion on Day 1, followed by placebo infusions every other week on Day 15 and Day 29 of treatment / relapse retreatment
- Single administration MIJ821 0.16 mg/kg, one infusion on Day 1, followed by Placebo infusions every other week on Day 15 and Day 29 of treatment / relapse retreatment

In all treatment arms, investigational treatment will be administered by intravenous infusion every other week, 3 infusions in total during the placebo-controlled double-blind Core, 6-week period of the study.

### 6.1.4 Treatment duration

One course of treatment in the core and extension period is defined as 3 infusions administered bi-weekly (Day 1; Day 15; Day 29).

#### Core Period

All participants who are randomized in the double-blind Core Period will receive three doses of investigational treatment or placebo once every 2 weeks over a total period of 6 weeks.

#### Extension Period

If relapse criteria are met during the Extension Period, participants will be treated with the same blinded dose and regimen they received during the Core period, receiving three i.v. infusions of investigational treatment once every 2 weeks, for a total period of 6 weeks. Participants receiving placebo in the Core Period, will be randomized in a blinded manner at the time of the initial randomization to one of the active treatment arms to receive treatment for relapse in the Extension Period in case they meet the required criteria at the End of Core (see [Section 3.4](#) for more details).

Only one course of three i.v. infusions of investigational treatment once every 2 weeks will take place in the extension. No second course of retreatment will be allowed. In case of clinical worsening after retreatment for relapse, the patient would not receive further retreatment with

the study drug. Patient will be managed as per see [Section 3.3](#) subsection Follow up duration and [Section 3.4](#) subsection Relapse and Clinical Worsening.

Once the dose and dose regimen for Phase 3 have been selected following completion of the interim analysis, participants experiencing a relapse who have not yet started retreatment will receive the selected Phase 3 dose and regimen in a dose-blinded manner. Patients who have already started treatment for the relapse will continue on the originally assigned dose.

## **6.2 Other treatment(s)**

### **6.2.1 Concomitant therapy**

All participants must receive pharmacological antidepressant therapy during the Core Treatment Period and 52 weeks Extension Period. Pharmacological treatment may include an antidepressant, or antidepressant plus augmentation therapy (e.g. antipsychotics, lithium, etc). Dosage titration or adjustments of standard-of-care antidepressant treatment occurring during the first 2 weeks of double-blind treatment are allowed, if needed, with dosages maintained thereafter during the Core period.

Psychotherapy will also be allowed and any change must be appropriately documented in the source records and CRF.

Each concomitant drug must be individually assessed against all exclusion criteria/prohibited medication.

During the Extension Period, pharmacological antidepressant therapy can be modified only for non responders or participants who did not achieve remission (see [Section 3.2](#) for more details).

Those participants, who are classified as a responder or remitter at the End of the Core Period must maintain a stable SoC (see [Section 3.2](#) for more details). In case of a relapse, the SoC pharmacological treatment can be adjusted, if needed, during the first 2 weeks of retreatment. Participants may or may not be hospitalized for the treatment of relapse (as per clinical judgment and local practices).

Participants who are responder or remitter at the End of the Core Period, and relapse during the Extension Period but do not meet the weight requirements of 50-120kg (inclusive) to be retreated in case of relapse, may change their SoC, as required, and should discontinue the Extension as defined in [Section 3.3](#) Follow-up Duration.

All medications, procedures, and significant non-drug therapies (including physical therapy and blood transfusions) administered after the participant was enrolled into the study must be recorded on the appropriate Case Report Forms (CRFs).

## **Potential interactions**

Based on nonclinical information, MIJ821 is predicted to be eliminated predominately by oxidative metabolism *via* CYP2D6 (64% of elimination). Inhibition of the elimination pathways may lead to an increase of MIJ821 exposure. The following investigations have been executed to assess the potential drug-drug interaction on the major elimination pathway *via* CYP2D6:

- The impact of strong CYP2D6 inhibitors (fluoxetine, paroxetine and bupropion) on the exposure of MIJ821 has been investigated in drug-drug interaction (DDI) simulations by means of the SimCYP® software. The simulated Cmax values were ≤ 1.3-fold higher in the presence of fluoxetine or paroxetine and the AUC values ≤ 2-fold for all CYP2D6 genotypes (poor, extensive, or ultra-metabolizers). At doses ≤ 0.16 mg/kg, the resulting mean exposure in the presence of strong CYP2D6 inhibitors are within the exposure range investigated in the FiH study (CMIJ821X2101, doses: 0.016, 0.048, 0.16, 0.24, 0.32 and 0.48 mg/kg). For the strong CYP2D6 inhibitor bupropion, no drug-drug interaction was estimated.
- Furthermore, in the PoC study (CMIJ821X2201, doses: 0.16 and 0.32 mg/kg), approximately 70% of patients received at least one CYP2D6 inhibitor (weak to strong CYP2D6 inhibitor or combinations of them). The Cmax values at both doses and the AUC values at 0.16 mg/kg do not exceed the exposure range determined in the FiH study.

Based on overall clinical experiences (CMIJ821X2101, CMIJ821X2201), the totality of the safety data suggest that MIJ821 is generally safe and well tolerated and observed adverse events were transient. The risk of an overdose or unexpected adverse events due to an exposure increase by CYP2D6 inhibition is considered to be low for the proposed MIJ821 doses being less or equal to 0.16 mg/kg. In conclusion, CYP2D6 inhibitors are allowed as co-medications. Nevertheless, caution has to be taken when strong CYP2D6 inhibitors are administered (see [Section 6.2.1.1](#)). All concomitant medications will be recorded.

Based on nonclinical information, MIJ821 may affect the elimination of compounds eliminated predominantly via CYP3A4 and CYP2D6. The impact of MIJ821 on the exposure of midazolam (CYP3A4 substrate) and desipramine (CYP2D6 substrate) has been investigated in drug-drug interaction (DDI) simulations by means of the SimCYP® software. No exposure increase of both probe substrates has been estimated at the highest tested MIJ821 dose of 0.48 mg/kg. Therefore, the risk of an overdose or unexpected adverse events of co-administered sensitive CYP3A4 and CYP2D6 substrates is considered to be not significant at MIJ821 doses ≤ 0.16 mg/kg.

#### **6.2.1.1 Permitted concomitant therapy requiring caution and/or action**

The investigator should instruct the participant to notify the study site about any new medications he/she takes after the participant is randomized in the study. All medications, procedures and significant non-drug therapies administered after the participant is enrolled into the study must be recorded.

The following medications should be administered with caution due to safety reasons and/or potential confounding factor for safety assessments.

- Antihypertensive medications should preferably be taken in the morning before dosing.
- Any benzodiazepines (including alprazolam and midazolam) are permitted at dosages up to the equivalent of 6 mg/day of lorazepam, for episodic or chronic use (see below for Benzodiazepines with their corresponding maximum dosages). They should not be taken within 12 hours of each study visit and for/within 4 hours after dosing (see [Table 6-2](#)), unless given as a rescue medication - see [Section 6.2.3](#) for more details
- Cough decongestants are allowed, but should not be taken within 12 hours of each study visit and for/within 4 hours after dosing.

- Benzotropine and diphenhydramine can only be used on a PRN basis and not within 12 hours of each study visit.
- Participants must not use alcohol, cannabis or psychostimulants (amphetamines, methylphenidate, modafanil, armodafinil etc.) within 24 hours before each study visit and 24 hours after end of infusion. If the use is identified by a urine test and confirmed by the assessment of the investigator or delegate at the visit (see [Section 8.4.1](#) for details), or if a participant appears intoxicated, the visit should be delayed as per the permitted visit window see [Section 8](#) for more details.
- Opioids must not be used within 24 hours before each study visit and 24 hours after end of infusion.
- Inhaled, intranasal, topical, and ophthalmic steroids are allowed. Intermittent oral, i.m./i.v. corticosteroids are permitted (chronic use prohibited).
- Trazodone must not be used within 24 hours before each study visit and 24 hours after end of infusion.
- For patients taking strong CYP2D6 inhibitors (berberine, bupropion, dacomitinib, fluoxetine, paroxetine, quinidine), the infusion period should be monitored with extra caution. All safety observations occurred during or after the end of infusion should be carefully observed for increased or unexpected frequency and severity. Infusion interruptions (i.v. infusion lasts less than 40 minutes), treatment interruptions (when subsequent i.v. dosing(s) is not performed) or study treatment discontinuation may apply in case of a safety concern, as defined in [Sections 6.6.2](#), [Section 9.1.1](#), [Section 10.2](#), and [Section 16](#).

Examples of Benzodiazepines with their corresponding maximum dosages:

- Lorazepam administered i.m. or p.o. (maximum daily dose 6 mg)
- Midazolam administered i.m. or p.o. (maximum daily doses 0.2 to 0.25 mg/kg not to exceed 20 mg)
- Clonazepam administered p.o. (maximum daily dose 4 mg)
- Alprazolam administered p.o. (maximum daily dose 4 mg in divided doses)

In case of a prohibited use, visit reschedule should be considered as per the permitted visit window - see [Section 8](#) for more details.

Each medication should be evaluated for the potential additive effect(s) of sedation, dissociation, suicidality, cardiovascular and respiratory effects, impact on memory and cognitive functions. Medications with a potential impact should be avoided for at least one half-life before each study visit and one half-life after each study drug administration.

### 6.2.2 Prohibited medication

Use of the treatments displayed in the below table are not allowed at the time points listed.

This list of medications is not all-inclusive. Each medication should be evaluated for the potential additive effect(s) of sedation, dissociation, suicidality, cardiovascular and respiratory effects, as well as impact on memory and cognitive functions. Medications with a potential impact should be avoided for at least one half-life of the medication before each study visit and one half-life after each study drug administration.

**Table 6-2 Prohibited medication**

Medication	Prohibition period	Action taken to study treatment***	Reason
Ketamine Esketamine	2 months before Screening and during the whole study duration (Core and Extension)	Discontinue study treatment if in the Core or discontinue study if in the Extension	Safety and PD interaction -additive effects (NMDA receptor antagonists)
Electroconvulsive therapy (ECT), transcranial magnetic stimulation (TMS), Deep brain stimulation (DBS), and Vagus nerve stimulation (VNS)	After Screening and during the whole study duration (Core and Extension)	Discontinue study treatment if in the Core or discontinue the study if in the Extension	PD interaction
Amantadine	After Screening and during the whole study duration (Core and Extension)	Discontinue study treatment if in the Core or Discontinue the study if in the Extension	Safety (CNS additive effects) and PD interaction (weak non-competitive NMDA receptor antagonist)
Monoamine oxidase inhibitors (MAOIs)	14 days before Screening, during the Core, and during the time of relapse retreatment (including 14 days before retreatment)	None	Safety (additive risk of hypertension effect and potential for precipitating hypertensive crisis) and PD interaction
Citalopram and Escitalopram	After Screening, during Core, and during the time of relapse retreatment + 1 week after last MIJ821 dosing	None	Safety (additive risk of QT prolongation, known risk of Torsades de Pointes)
Medications with a "Known Risk of Torsades de Pointes" per www.qtdrugs.org and Table 16-7	7 days before Screening, during Core, and during the time of relapse retreatment + 1 week after last MIJ821 dosing	None	Safety (additive risk of QT prolongation, risk of Torsades de Pointes)
Amitriptyline, Nortriptyline	Within 24 hours prior to each study visit**and up to at least 4 h after end of infusion	None	Safety (additive risk of QT prolongation, risk of Torsades de Pointes)
Quetiapine	Within 12 hours prior to each study visit**and up to at least 4 h after end of infusion	None	Safety (additive risk of QT prolongation, risk of Torsades de Pointes)
Oral and Systemic Hormonal Contraceptives for contraception purposes	After Screening, during Core, and during the time of relapse retreatment+ 1 week after last MIJ821 dosing	None	Not accepted as highly effective contraception method until a dedicated clinical study shows no drug-drug interaction between MIJ821 and hormonal contraceptives
Systemic Corticosteroids	Chronic use is prohibited after Screening, during Core, and during the time of relapse retreatment	None	Safety (additive cardiovascular and neuropsychiatric effects)
Benzodiazepines (including alprazolam and	Within 12 hours prior to each study visit** and up	None*	Safety (additive sedative effect) and confounding

Medication	Prohibition period	Action taken to study treatment***	Reason
midazolam) at dose equivalent of up to 6 mg/d Lorazepam	to at least 4 h after end of infusion, unless given as a rescue medication to treat agitation , anxiety or aggressive behavior		effect for safety assessments
Cough decongestants	Within 12 hours prior to each study visit**and up to at least 4 h after end of infusion	None*	Safety (additive sedative effects) and confounding effect for safety assessments
Benztropine and diphenhydramine	Within 12 hours prior to each study visit**. Continuous use is prohibited	None*	Safety (additive sedative effect) and confounding effect for safety assessments
Trazadone	Within 24 hours prior to and 24 hours after each study drug infusion	None*	Safety (additive Risk of QT prolongation)
Alcohol	Within 24 hours prior to each study visit and 24 hours after end of infusion	None*	Safety (additive sedative and CNS effects), confounding effect for safety and efficacy assessments
Cannabis and Psychostimulants (amphetamines, methylphenidate, andmodafinil, armodafinil etc.)	Within 24 hours prior to each study visit and 24 hours after end of infusion	None*	Safety (additive CNS effects), confounding effect for safety and efficacy assessments
Opioids	Within 24 hours prior to each study visit and 24 hours after end of infusion	None*	Safety (additive sedative and CNS effects), confounding effect for safety and efficacy assessments

\* In case of a prohibited use or when a participant appears intoxicated at the visit (e.g., alcohol, etc.), visit reschedule should be considered as per the permitted visit window - see [Section 8.4.1](#) for more details

\*\* With the exception of the screening visit

\*\*\* Participants who are in the two-month follow-up period should continue the follow-up even in case they are taking prohibited medications.

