### 3.3 Double-blind Extension Period

After completing the double-blind Core Period, all participants will enter the Extension Period for a minimum of 8 weeks and a maximum of 52 weeks.

Those participants who are not responders and not remitters at the end of the Core Period (see in this section, subsection Extension Follow-up duration for more details ), will be observed in an abbreviated Extension Period lasting 8 weeks only to obtain safety data and evaluate withdrawal and rebound effects of MIJ821. Because those participants did not respond to the treatment as defined in [Section 3.2](#) in the first instance, no retreatment will be provided in case of relapse. Those participants are allowed to adjust their SoC in their 8 weeks Extension Period, as necessary.

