### SoC can be adjusted or modified after the relapse retreatment, as clinically warranted. Extension Follow-up Duration

[figure not shown]
All participants must complete a follow-up period after the End of Core Period visit (Day 43):

- For participants who are neither remitters nor responders at the End of Core Period (Day 43) [Section 3.2](#), the follow up will last 8 weeks and consists of 3 mandatory visits (the 2 weeks Follow-up visit, the 4 weeks Follow up visit and the End of Study visit occurring 8 weeks after Day 43)
- For participants who are responders or remitters at the End of the Core Period (Day 43), and who do not experience any relapse, the Extension Period will last 52 weeks. This will consist of the 2 weeks Follow-up visit, the 4 weeks Follow-up visit, and thereafter Follow-up visits occurring every 4 weeks up to End of Study visit at Week 52
- Participants who are responders or remitters at the End of the Core Period (Day 43), and who relapse during the Extension Period, will receive one course of retreatment with MIJ821.
  - After that course of retreatment:
    - The participant will resume the 4 weekly Follow-up visit schedule (E.g., if the 6 weeks relapse retreatment period occurred from week 19 to 25, the participant will not perform visits week 20 and week 24, and will resume the follow-up at week 28).

- The duration of the follow up will be as per the initial schedule up to Week 52 or clinical worsening, whichever comes first, but they must complete at least 8 weeks follow-up period (see [Section 6.1.4](#)). Signs of clinical worsening may include worsening of depressive mood, need for SoC adjustments, a suicidal attempt, hospitalization for depression or suicidal ideation or behavior. For patient management see [Section 3.4](#), subsection Relapse and Clinical Worsening.
- Participants who are responders or remitters at the End of the Core Period (Day 43), and who relapse during the Extension Period but do not meet the weight requirements of 50-120kg (inclusive), cannot be retreated for the relapse and must be discontinued. The Extension period for these participants should last at least 8 weeks before the discontinuation.

The total duration of the Extension Period is 52 weeks, maximum. Therefore, the last date of confirmed relapse enabling access to the retreatment period is 38 weeks. If a participant relapses on or after that date, the participant must complete the End of Study visit as soon as possible.

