  - Post-dose systolic blood pressure of  $\geq 200$  mmHg and/or the DBP is  $\geq 120$  mmHg confirmed by triplicate reading (at least one value should confirm the blood pressure increase above the defined thresholds).

If discontinuation of study treatment occurs, the investigator should make a reasonable effort to understand and record the primary reason for the participant's premature discontinuation of study treatment.

Participants who discontinue study treatment or who decide they do not wish to participate in the study further should NOT be considered withdrawn from the study UNLESS they withdraw their consent (see [Section 9.1.2](#)). Where possible, they should return for the assessments indicated in the Assessment Schedule. If they fail to return for these assessments for unknown reasons, every effort (e.g. telephone, e-mail, letter) should be made to contact the participant/pre-designated contact as specified in the lost to follow-up section.

If the participant cannot or is unwilling to attend any visit(s), the site staff should maintain regular telephone contact with the participant, or with a person pre-designated by the participant. This telephone contact should preferably be done according to the study visit schedule.

Following study treatment discontinuation (no further infusions planned), participants should be followed for two months beyond the 6 week Core Period (Follow-up Period).

Participants who discontinue study treatment during the Core Period should return at every scheduled visit until the End of the 6 week Core Period. The list of assessments should be kept as planned with the following exceptions: ECG and vital signs to be measured (triplicates required), no PK sampling collection, and all assessments that are repeated several times in one day should be done only once [REDACTED]

[REDACTED] Participants will then enter the two months Follow-up Period.

Participants who discontinue study retreatment during the Extension Period should return for the End of Relapse visit and subsequently enter the two month Follow-up Period.

If an onsite visit is not possible, then telephone visits should be conducted and collected at minimum the following:

- New / concomitant treatments
- Adverse Events / Serious Adverse Events

The investigator must also contact the IRT to register the participant's discontinuation from study treatment.

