  - Interruption of intravenous infusion (prior to the complete 40 min duration)
  - Drug interruption/withdrawal (no further intravenous infusions)
6. Its outcome (e. g. recovery status or whether it was fatal)

Conditions that were already present at the time of informed consent should be recorded in medical history of the participant.

Adverse events (including lab abnormalities that constitute AEs) should be described using a diagnosis whenever possible, rather than individual underlying signs and symptoms.

Adverse event monitoring should be continued throughout the study until the End of Study visit.

Once an adverse event is detected, it must be followed until its resolution or until it is judged to be permanent (e.g. continuing at the End of the study), and assessment must be made at each visit (or more frequently, if necessary) of any changes in severity, the suspected relationship to the interventions required to treat it, and the outcome.

Information about adverse drug reactions for the investigational drug can be found in the Investigator's Brochure (IB).

Abnormal laboratory values or test results constitute adverse events only if they fulfill at least one of the following criteria:

- they induce clinical signs or symptoms
- they are considered clinically significant
- they require therapy

Clinically significant abnormal laboratory values or test results must be identified through a review of values outside of normal ranges/clinically notable ranges, significant changes from baseline or the previous visit, or values which are considered to be non-typical in participant

with the underlying disease. Alert ranges for laboratory and other test abnormalities are included in [Section 16.1](#).

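### Table 6-2 takes Extension participants off the study after ketamine, esketamine, neurostimulation or amantadine, contradicting the follow-up rules in Protocol Sections 3.3, 9.1.1 and 9.2

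*Protocol*

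**What the plan says.** Protocol Table 6-2 sets the action for ketamine and esketamine as "Discontinue study treatment if in the Core or discontinue study if in the Extension". The row for ECT, TMS, DBS and VNS reads "Discontinue study treatment if in the Core or discontinue the study if in the Extension", and the amantadine row has the same effect. A three-asterisk footnote on the action column adds: "Participants who are in the two-month follow-up period should continue the follow-up even in case they are taking prohibited medications".

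Other parts of the protocol point the other way:

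- Section 9.1.1 lists use of a prohibited treatment, with a reference to Section 6.2.2, among the reasons for stopping study treatment. It then says that participants who stop treatment "should NOT be considered withdrawn from the study UNLESS they withdraw their consent". Those who stop retreatment in the Extension have an End of Relapse visit and then two months of follow-up. Where a site visit is not possible, telephone contact is to capture at least AEs, SAEs and new or concomitant treatments.
- Section 3.3 says that after the Core "all participants will enter the Extension Period for a minimum of 8 weeks and a maximum of 52 weeks". It also requires at least 8 weeks of follow-up after retreatment, and at least 8 weeks of Extension even for relapsers who cannot be retreated because of their weight.
- Section 9.2 repeats the 8-week minimum after the End of Core for all randomized or treated participants.
- Section 6.2.3 allows medication listed in Table 6-2 to be given as rescue at any time when clinically warranted.

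On the end of collection, Section 10.1.1 states: "Adverse event monitoring should be continued throughout the study until the End of Study visit". Section 10.1.3 sets the same endpoint for SAEs. Section 8 gives premature leavers a final visit as soon as possible.

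**The concern.** A site cannot apply both Table 6-2 and Section 9.1.1 to the same participant. One ends study participation; the other ends dosing and keeps the participant under observation. The difference decides whether new AEs and SAEs are still collected.

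This matters most for suicidality, which is an AE of special interest. Under Section 10.1.3, suicidality and depression SAEs are not unblinded or expedited case by case. The stated safeguard is aggregate DMC review, including comparison with placebo, and that review depends on continued collection. Section 1 places ECT in severe depression needing a rapid response, and Section 1.1 places esketamine in depression with acute suicidality. Use of these two is therefore plausibly linked to deterioration. The documents make no such link for TMS, DBS, VNS or amantadine.

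**Working it through.** **Step 1. Who does the footnote cover?** It names only participants in the two-month follow-up. Section 9.2 sets the 8-week follow-up and the 52-week Extension side by side as alternatives. On the plain reading, a non-responder in the 8-week Extension is covered. A responder or remitter in the 52-week Extension, or a participant in retreatment, is not.

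**Step 2. Responder or remitter in the 52-week Extension, not in retreatment.** Inputs: End of Core is Day 43, the last Core infusion is Day 29, and the minimum Extension is 8 weeks (Section 3.3, Table 8-1). For use at Extension week w, the shortfall against the minimum is 8 − w weeks, and zero from Week 8.

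- w = 2 is Day 43 + 14 = Day 57, which is 57 − 29 = 28 days after the last infusion. Shortfall: 8 − 2 = 6 weeks.
- w = 4: shortfall 8 − 4 = 4 weeks.
- w = 8 or later: no shortfall. What remains is the tension with Section 9.1.1, weaker here because no course of treatment is under way.

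A non-responder given the same treatment at Week 2 stays in follow-up under the footnote.

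**Step 3. Participant in retreatment.** Inputs: infusions on retreatment Days 1, 15 and 29; End of Retreatment on Day 43; TEAE window to 2 weeks after the last dose (SAP Section 2.6.1); two months taken as 8 weeks.

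- Under Table 6-2, use on retreatment Day 2 leads to study discontinuation one day after an infusion. With Day 1 as the last dose, the TEAE window runs to Day 1 + 14 = Day 15. Up to 15 − 2 = 13 days of it would be unobserved, depending on how soon the final visit takes place.
- Under Section 9.1.1, the same participant is followed for about 8 more weeks if the End of Relapse visit is immediate. If that visit stays at Day 43 and the use was on Day 1, follow-up is 6 + 8 = 14 weeks.

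So Table 6-2 gives nothing beyond the final visit, where Section 9.1.1 gives roughly 8 to 14 weeks.

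**Step 4. Rescue use.** Section 6.2.3 permits the listed medications as rescue. Table 6-2 does not say whether such use in the Extension also triggers study discontinuation.

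**Step 5. The Week 38 limit.** Section 3.3 says "The total duration of the Extension Period is 52 weeks, maximum". Subtracting the 6-week retreatment course and the 8-week minimum follow-up gives 52 − 6 − 8 = 38, which reproduces the stated limit exactly. (Counting the 8 weeks from the last retreatment infusion, 4 weeks into the course, would give 52 − 4 − 8 = 40, which does not match.) Section 3.3 makes Week 38 the last date of confirmed relapse that allows retreatment, then adds: "If a participant relapses on or after that date, the participant must complete the End of Study visit as soon as possible". A relapse at exactly Week 38 falls under both rules.

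A late relapser who was not retreated is at least 38 weeks past the End of Core, and 38 + 2 = 40 weeks past the Day 29 infusion. The 8-week minimum is exceeded by at least 38 − 8 = 30 weeks. Planned observation is shortened by at most 52 − 38 = 14 weeks (14/52 = 27%).

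**The case against.** The strongest defence is that the footnote can be read more widely. It hangs on the column heading, so it applies to every row. Section 9.1.1 sends anyone with no further infusions planned into follow-up until two months beyond the Core. A responder who loses access to retreatment could be placed there, and the footnote would then keep that person in. This reading is possible, so early exit in the Week 2 example is not certain. But it leaves the study-discontinuation instruction without effect in the first 8 weeks of the Extension, which the table does not say. It also cannot help a participant retreated later, when two months beyond the Core have already passed; that case rests on the separate retreatment sentence in Section 9.1.1, which the table contradicts.

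A second objection is that little is lost. This stands in part. A final visit is done, AEs already detected are followed to resolution or until judged permanent, and follow-up information on reported SAEs is still required. Only new events after the final visit are lost. Day 57 also lies outside the Core TEAE window, which closes at Day 29 + 14 = Day 43, so that example touches no planned between-arm TEAE summary. The retreatment example does fall inside a TEAE window.

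A reader might go further and infer that collection stops when risk is highest, that the worst outcomes are removed, or that late suicidality SAEs are under-counted differently by arm. The documents give no risk over time, no expected frequency of these treatments and no affected between-arm analysis. They also count suicide attempt and hospitalization for suicide prevention among the relapse criteria, so such events can be recorded before exit. These remain conjectures.

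**Conclusion.** The contradiction is real for responders and remitters in the 52-week Extension and for participants in retreatment. It is clearest in retreatment, where the two rules differ by about 8 to 14 weeks of observation, and in the first 8 weeks of the Extension, where the promised minimum can be missed by up to 6 weeks in the Week 2 example. This rests on reading the footnote as written and on taking two months as 8 weeks. The number of participants affected is unknown and may be small.

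The late-relapse exit might be taken as a second conflict with the follow-up rules. It is not. Week 38 follows from the protocol's own durations, every stated minimum has passed, and longer observation there would be a design preference. Only the overlap at exactly Week 38 needs correcting.

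**What to change.** Reconcile Table 6-2 with Sections 3.3, 6.2.3, 9.1.1 and 9.2 as to data collection. Extend the footnote to all Extension and retreatment participants, so that AEs, SAEs and concomitant treatments continue to be collected for at least the 8 weeks of follow-up the protocol already promises. Scheduled visits or the telephone contact in Section 9.1.1 would serve. State whether Table 6-2 medication given as rescue under Section 6.2.3 falls under the same action. In Section 3.3, state which rule governs a relapse confirmed at exactly Week 38. The treatment, prohibition and retreatment rules themselves are for the sponsor to reconcile; no change to them is proposed here.

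The cost is amendment wording. The means of contact already exist in the protocol. The downside is that a few participants stay in follow-up longer.
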